Although the pathophysiology of autism remains poorly understood, the accumulated data suggest that the aetiology may potentially include immune dysregulation (see Onore et al., 2012). Extensive research points to immune system abnormalities, including active brain neuroinflammation, pro-inflammatory cytokines enhanced profiles, immune cells dysfunction, and the autoimmunity directly associated with an increase in behavioural disorders. Studies have shown an ongoing neuroinflammatory process with pronounced activation of microglia and astroglia in the cerebral cortex, alba and cerebellum of patients with autism. A unique profile of pro-inflammatory cytokines in autistic patients was recorded in the cerebrospinal fluid, including a marked increase in macrophage chemoattractant protein-1 and in peripheral plasma, such as significantly elevated levels of interleukin (IL) -1 β , IL -8 and IL-12p40. Additional studies have shown altered function in subsets of immune cells (Ashwood P, Corbett BA, Kantor A, Schulman H, Van de Water J, Amaral DG. In search of cellular immunophenotypes in the blood of children with autism. , Enstrom AM, Lit L, Onore CE, Gregg JP, Hansen RL, Pessah IN, Hertz-Picciotto I, Van de Water JA, Sharp FR, Ashwood P. Altered gene expression and function of peripheral blood natural killer cells in children with autism. *Brain Behav Immun.* 2009.) That leads to an inappropriate or ineffective immune response in autism. Different "housekeeping" antibodies enter into reaction with proteins found in the central nervous system of the children with autism associated with an autoimmune process. Taken together, these data suggest that immune dysfunction is not only a symptom or associated disease but also an indicant of the underlying pathophysiological process, so targeting this pathology and changing neuroimmune reactions can be effective from a therapeutic point of view. However, only a few clinical research studies of anti-inflammatory drugs are aimed at correcting immune dysregulation or continuing neuroinflammation in autism. Due to its known ability to alter immune response, cord blood mononuclear cells can be a new therapeutic effect in clinical practice to normalize the immune response characteristic of some children with autism.

There are behavioural, educational, medical, health care and optional methods of autism care. However, there is no definitive standard treatment for children with autism. Stem cell therapy

has shown great promise in modern treatment and rehabilitation of patients with autism. Preclinical research studies have reported that transplantation of human cord blood mononuclear cells (CBMNC) in animals in models of cerebral ischemia promotes functional recovery by improving local blood perfusion in damaged areas through angiogenesis (Park DH, Borlongan CV, Willing AE, Eve DJ, Cruz LE, Sanberg CD, Chung YG, Sanberg PR, Cell Transplant, 2009)

Some studies have confirmed that cerebral hypoperfusion is associated with many of leading autism symptoms (Wilcox J, Tsuang MT, Ledger E, Algeo J, Schnurr T. Brain perfusion in autism varies with age. Neuropsychobiology. 2002;). Generalized brain hypoperfusion, achieved in the frontal and prefrontal areas, was observed in children with autism and is associated with cognitive and neuropsychological defects. Besides, a decrease in cerebral perfusion, especially in the temporal-parietal areas, is associated with a cognitive deficit, such as speech deficits, cognitive disorder or object representation or anomalous perception and responses to sensory stimuli. Inadequate perfusion leading to hypoxia of brain tissue had not only caused apoptosis and necrosis of neurons but also led to abnormal brain tissue metabolism and accumulation of pathological doses of neurotransmitters. As a result of the systemic administration of stem cells CD34 + cord blood to overcome ischemia in vitro and in animals, therapeutic angiogenesis has been proven experimentally. Also, it was proved that the endothelial progenitor cell contained in the population of CD34 + cells had the ability to initiate angiogenesis in ischemic tissues. Circulating CD34 + progenitors in the PC with endothelium development potential has turned into new endothelial cells to either restore the damaged endothelium wall or germinate a new vascular structure. Moreover, human CD34 + cells and hematopoietic progenitors could secrete multiple angiogenic factors, such as vascular endothelium growth factor (VEGF), HGF, and insulin-like growth factor-1.

The preclinical research study data on the mononuclear core blood cells ability to stimulate neoangiogenesis in ischemic areas allow introducing the method of injecting these cells in cases of brain hypoperfusion or hypoxia to limit and reduce the area of ischemic tissue degeneration.

To assess the therapeutic efficacy of using core blood cells, during the research studies the CARS, CGI and ABC scales were used. CARS provides descriptive information about pathological behaviour and classifies severity in children with autism, while the CGI scale, as a global measure, indicates a noticeable overall treatment effect. However, further research will need to extend the rating scales to standardize the diagnosis and treatment of autism in detail.

In 2011, a Chinese research group from the Shenzhen Beike Bio-Technology Co. conducted a scientific clinical research study of the use of intravenous mononuclear cord blood cells in patients diagnosed with autism. In total, 37 patients aged 3 to 12 years were tested. There were 3 clinical groups: Group 1 consisted of 14 patients receiving the injections of mononuclear cord blood cells

at a dosage of 2 million cells per 1 kg of patient weight (1 intravenous injection, 3 intrathecal with an interval of 5-7 weeks). Group 2 consisting of 9 patients receiving the injections of mononuclear cord blood cells at a dosage of 2 million cells per 1 kg of patient weight and mesenchymal stem cells at a dosage of 1 million cells per 1 kg of patient weight (2 intrathecal and intramuscular injections and 2 intrathecal injections solely). Patients of Groups 1 and 2 received standard rehabilitation therapy. Group 3 consisted of 14 patients receiving standard rehabilitation therapy. The evaluation was conducted 24 weeks after the course of injections. During the treatment, all patients had normal and stable vitals. At the periods of injections or period after them. No allergic or immunological reactions were observed in any patient. There were no deviations from the normal ranges or significant changes in the laboratory indicators of the liver and kidneys functioning, in comparison with the initial level (ALAT, ASAT, bilirubin, urea, and creatinine). Evaluation of the psychological status was made on the CARS scale. The total CARS score was significantly reduced in the Group 2 (a decline of 37.9%); in Group 1, the indicator decreased by 20.0%; in Group 3, i.e. the control group, the indicator decreased by 13.7%. The initial CARS score indicator in each group was at the level of 45. In Groups 1 and 2, there were improvements in behaviour defined for the "Attitude to people", "Body use", "Visual response", "Taste, smell, the reaction on touch and use" and "General Impressions" sub-scales. Those changes were not observed in the control group. The research study proved the safety and effectiveness of the use of cord blood mononuclear cells in the complex treatment of patients. (Transplantation of human cord blood mononuclear cells and umbilical cord-derived mesenchymal stem cells in autism Yong-Tao Lv, Yun Zhang, Min Liu,¹ Jia-na-ti Qiuwaxi,² Paul Ashwood,³ Sungho Charles Cho,⁴ Ying Huan,¹ Ru-Cun Ge,¹ Xing-Wang Chen,¹ Zhao-Jing Wang,² Byung-Jo Kim,⁵ and Xiang Hucorresponding).

\

CLINICAL PURPOSES

Estimation of the safety and efficiency of the method of transfusion of umbilical blood hemopoetic cells to patients with diagnosed autism spectrum disorder without depending on the degrees of compatibility of donor and recipient.

TASKS

1. Develop an algorithm for using the method of transfusion of hematopoietic umbilical cord blood cells in the treatment of patients with autistic type disorder.
2. To formulate criteria for the selection of patients for this technique.

3. To analyze the efficacy and safety of transfusion of hematopoietic cord blood cells in patients with autistic type disorder using rating scales.
4. Introduce the method of transfusion of cord blood hematopoietic cells to patients with autistic type disorder in the complex therapy of patients with autistic type disorder.

OBJECT OF STUDY

The protocol for testing the method will be carried out on 10 patients with autism spectrum disorder by transfusion of hematopoietic cord blood cells. As a control group, 10 patients with a similar pathology will be examined, comparable in age, gender and degree of autistic disorder according to the “paracopy” type against the background of standard therapy.

Type of study: interventional, prospective, non-randomized with a control group.

Patient selection criteria (indications for this type of treatment):

- age of the patient is from 3 to 15 years.
- Diagnosis: autistic disorder.
- Systemic speech underdevelopment
- The presence of attention deficit hyperactivity disorder as a comorbid state
- Cognitive impairment

Patient exclusion criteria (contraindications for this type of treatment):

- The patient's under 3 years, after 15 years;
- The presence of organic pathology of the brain according to CT, MRI
- The presence of the following diseases in the anamnesis: heart failure in the stage of decompensation, a history of stroke less than 1 year ago, anemia and other blood diseases;
- Decompensation of chronic and endocrinological diseases;
- Acute respiratory viral and bacterial infections, period less than 1 month after the acute phase.
- HIV infection, hepatitis B and C.
- Cancer, chemotherapy and history of cancer;
- Tuberculosis.
- Severe form of intellectual disability as a concomitant disease (diagnosis can be ignored, according to the decision of the Medical Committee of the Center);
- Cerebral palsy.
- Increased convulsive readiness, epilepsy.

Indications and contraindications to this type of treatment for each patient are determined at a consultation of doctors with the participation of a paediatrician or a psychologist (psychiatrist), and transfusiologist.

Research methods

Evaluation scales CARS, ATEC (to assess the dynamics). Neuropsychological examination, examination of a speech therapist-pathologist. Assessment of neurological status. Determination of the immune status by flow cytometry (CD3; CD4; CD8; CD19; CD16-56). Determination of the level of cytokines in peripheral blood: interleukin 1 beta, interleukin 6, tumor necrosis factor alpha, interleukin 8, gamma interferon. Determination of the HLA genotype of the subject parents and siblings.

The results will be statistically processed using parametric and non-parametric statistics methods using STATA version 9.0, Statistica for Windows version 6.0 and MS Office Excel 2007. Changes from the start of therapy and after 1, 2, 6, 12 months will be compared using the Wilcoxon criterion, comparing data between the main group and the control group using non-parametric method, using the Mann-Whitney test (data are presented in Me - median format with an indication of 25% (q1) and 75% (q3) quartile.

Treatment protocol

Selection of patients and assessment of their psychological status, transfusion of umbilical cord blood HSC in the conditions of day hospital is carried out by specialists of the State budgetary institution of public health "Samara Regional Children's Clinical Hospital N.N. Ivanova Laboratory examination, selection of biomaterial will be carried out by the State Budgetary Institution "MC Dynasty".

Stage 1 - selection and examination of the patient, determination of indications and contraindications to this method of treatment is carried out by a child neurologist, pediatrician (pediatrician), medical psychologist. Assessment of autism disorder is carried out according to the assessment scales of CARS, ATEC.

A prerequisite for inclusion:

- diagnosed with autism spectrum disorder by a psychiatrist,
- Dispensary supervision by a child psychiatrist at the place of residence.

Mandatory general clinical trials (clinical and diagnostic laboratory):

- a) General clinical blood tests (erythrocytes, hemoglobin, platelets, clotting time, leukocytes + formula, COE) - shelf-life 14 days.
- b) general clinical urine test - shelf life 14 days.
- c) feces per helminth eggs - shelf life 14 days.
- d) blood type and rhesus factor.

A patient who meets the selection criteria and has no contraindications for this type of treatment enters into a protocol and signs an informed consent (or his/her legal representative).

Stage 2 - umbilical cord blood sampling. It is performed by a transfusion doctor of the State Budgetary Institution "MC Dynasty".

The selection criteria for the sample will be the following parameters:

1. Blood group compatibility by system AB0 and Rh
2. Infectious safety (negative HIV test results, hepatitis B and C, syphilis, herpes simplex virus, cytomegalovirus, toxoplasmosis)
3. No bacterial or fungal contamination.
4. Number of hematopoietic cells (mononuclears) in the range of 20-50 million cells per kg of patient weight.

Stage 3 - intravenous injection of hematopoietic cells in umbilical cord blood.

Preliminary examination of the patient and relatives:

- a) Determination of immune status by flow cytometry (SD3; SD4; SD8; SD19; SD16-56) - patient.
- b) Determination of cytokine levels in peripheral blood: interleukin 1 beta, interleukin 6, tumor necrosis factor alpha, interleukin 8, gamma-interferon - patient.
- c) Determination of HLA genotype by loci A, B, DRB1 - patient and parent, sibling.

The sample consists of a suspension of hematopoietic cells diluted in 10 ml 0.9% NaCl + 10 ml 6% hydroxyethyl starch in a disposable syringe labeled by the manufacturer (label).

The patient is injected in drops with the use of infusion. The rate of administration is 60 - 70 ml per hour. Immediately at the beginning of injection, a biological compatibility test should be performed.

Three-fold injection is planned at an interval of 1 month.

Possible area of application

Specialized hospitals.

Data to be obtained during implementation

- correct selection of criteria for selecting patients for treatment of patients with autism type disorder;
- developed algorithm for using the method of transfusion of hematopoietic cells of umbilical cord blood in complex therapy of patients with autism type disorders;
- information on the efficacy and safety of treatment of patients with autism-type disorder by transfusion of hematopoietic cells of umbilical cord blood;
- appropriateness and effectiveness of this method of treatment. To evaluate its impact on treatment tactics and results;
- Association of HLA genes with the development of autism spectrum disorders;
- relationship between immune status and cytokine profile and severity of the disease.

Therapy evaluation criteria

Evaluation of the effect of treatment is carried out 1, 2, 3 and 6 months after treatment.

Evaluation of the effect is carried out using the scales used in the introduction to the protocol, evaluation of the neurological and psychological status of the patient.

Evaluation of immune status indicators is carried out 6 months after the last injection.

Cytokine profile is assessed 1, 2, 3 months after the first injection.

Expected results:

It is assumed that transfusions of hematopoietic cord blood cells in patients with autism spectrum disorders will not cause adverse reactions and complications (safe) and will lead to improved social interaction and communication of patients, increased social adaptation, reduced stereotyping, increased self-service skills, increased cognitive functions.

STATISTICAL CONSIDERATIONS

This study will enroll autistic children age 3 to 15 years of age.

Participants will be carried out on 10 patients with autism spectrum disorder by transfusion of hematopoietic cord blood cells. As a control group, 10 patients with a similar pathology will be examined, comparable in age, gender and degree of autistic disorder according to the “paracopy” type against the background of standard therapy.

This is interventional, prospective, non-randomized with a control group study with three intravenous allogeneic, unrelated CB infusion in children ages 3-15 years with ASD/

The primary outcomes will be assessed 1, 2,3,6 and 12 months after the initial infusion in the sequence. Duration of study participation will be 12 months from the time of baseline infusion.

Accrual

It is estimated that up to 2-3 research participants will be enrolled each week and that approximately 4 weeks of accrual will be necessary to enroll 10 participants.

Study Duration

Research participants will be followed for safety for 12 months after the third study infusion.

Demographics and Baseline Characteristics

Demographics and baseline characteristics will be summarized for all research participants. Characteristics to be examined include age, sex, and baseline behavioral status (ATEK).

The results will be statistically processed using parametric and non-parametric statistics methods using STATA version 9.0, Statistica for Windows version 6.0 and MS Office Excel 2007. Changes from the start of therapy and after 1, 2, 6, 12 months will be compared using the Wilcoxon criterion, comparing data between the main group and the control group using non-parametric method, using the Mann-Whitney test (data are presented in Me - median format with an indication of 25% (q1) and 75% (q3) quartile.

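### Background therapy is stated only for the controls, and is neither matched, recorded nor adjusted for, so a difference in it would be credited to or subtracted from the cells

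*Combined protocol and SAP*

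**What the plan says.** OBJECT OF STUDY, repeated under STATISTICAL CONSIDERATIONS, describes the main group only by its cord blood infusions. The next sentence describes 10 controls "comparable in age, gender and degree of autistic disorder according to the" pairing scheme it names, examined on standard therapy. Those two passages are the only mentions of standard therapy in this trial, and neither defines it. The design is declared non-randomised.

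TASKS item 4 is to "Introduce the method of transfusion of cord blood hematopoietic cells to patients with autistic type disorder in the complex therapy", and the list of data to be obtained repeats that setting. Stage 1 of the treatment protocol makes supervision by a local child psychiatrist a prerequisite for inclusion.

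Research methods lists rating scales, specialist examinations, immune and cytokine measures and HLA typing. Demographics and Baseline Characteristics names age, sex and baseline ATEC. Neither mentions concurrent therapy. The between-group analysis is a Mann-Whitney test with no adjustment.

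The introductory account of the cited study states that "Patients of Groups 1 and 2 received standard rehabilitation therapy" and that its control group did too.

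**The concern.** If the cells are given within complex therapy, the question is what they add to other care. That contrast is defined only if the other care is alike in both groups, or at least known. Without randomisation, comparability rests on the named factors, and background therapy is not one of them.

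The three named factors do not stand in for it. Two children of the same age, sex and severity can differ in rehabilitation, speech or behavioural therapy and medication. That difference acts on the rate of change over follow-up, which is what the trial compares, so similar baseline scores would not reveal it. The local supervision requirement also suggests that part of each child's care lies outside the study centre.

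The cited study gave standard rehabilitation to all three of its groups; this plan does not say the same of its two. If therapy is not recorded as the trial runs, it will be hard to reconstruct reliably later, and an imbalance could be neither shown nor ruled out.

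**Working it through.** The plan states no target effect, standard deviation or power for its 10 + 10 children, so it has no figure of its own to reproduce. The size below is borrowed from the cited study as a guide.

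**Inputs** (introductory account of the three-group study)
- Baseline: "The initial CARS score indicator in each group was at the level of 45".
- Group 1, cord blood cells plus rehabilitation, and Group 3, rehabilitation only: "in Group 1, the indicator decreased by 20.0%; in Group 3, i.e. the control group, the indicator decreased by 13.7" per cent.
- Group 2, cord blood and mesenchymal cells plus rehabilitation: "The total CARS score was significantly reduced in the Group 2 (a decline of 37.9" per cent).

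**Step 1. Falls in CARS points** (baseline × percentage)
- Group 3: 45 × 0.137 = 6.165
- Group 1: 45 × 0.200 = 9.000
- Group 2: 45 × 0.379 = 17.055
- Group 1 minus Group 3: 2.835 points (6.3 percentage points)
- Group 2 minus Group 3: 10.890 points (24.2 percentage points)

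**Step 2. Control fall as a share of each cell group's fall**
- Against Group 1: 13.7 / 20.0 = 68.5%
- Against Group 2: 13.7 / 37.9 = 36.1%

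**Step 3. Imbalance in background therapy that would equal the Group 1 difference**

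Two assumptions are needed, and the documents support neither directly. First, benefit from background therapy is proportional to its intensity. Second, a share *f* of the 13.7% control fall is due to therapy. The rest is natural course, regression to the mean and rater expectation; the cited study had no untreated group from which to separate these. Let *r* be the infused group's background-therapy benefit relative to the controls'. With inactive cells,

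spurious difference = (r − 1) × f × 13.7 percentage points,

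and setting this equal to 6.3 gives r − 1 = 6.3 / (13.7 f).

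| f | Imbalance equal to 2.8 points | Effect of a 20% imbalance | As share of 2.835 |
|---|---|---|---|
| 1 | 6.3 / 13.7 = 46% | 0.20 × 6.165 = 1.23 points | 43% |
| 0.5 | 6.3 / 6.85 = 92% | 0.62 points | 22% |
| 0.25 | 6.3 / 3.425 = 184% | 0.31 points | 11% |

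**Step 4. The opposite direction.** Suppose the 2.835 points are a real cell effect and the infused children have less background therapy.
- f = 1: the effect is cancelled at r = 1 − 0.46 = 0.54.
- f = 0.5: it is cancelled at r = 1 − 0.92 = 0.08.
- f = 0.25: it cannot be fully cancelled. Even with no background therapy the loss is 0.25 × 6.165 = 1.54 points, or 54% of 2.835.

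**Step 5. The larger difference.** To equal the Group 2 difference with f = 1, the imbalance would have to be 24.2 / 13.7 = 177%.

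**The case against.** The strongest reply is that the add-on intent is already visible. The plan twice places the cells in complex therapy, and in a translated text the attachment of standard therapy to the control sentence may be only wording. This stands in part. A reader might infer that infused children go without standard therapy; the documents do not show that. They show only that the infused group's care is unspecified and not equalised. Likewise, the baseline list says what characteristics *include*, so it need not be exhaustive, but nothing else in the plan captures therapy.

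Three readings of the cited figures are tempting and unsupported:
- **That rehabilitation caused about two-thirds of the benefit seen with cells.** The 13.7% fall mixes therapy with natural course, regression to the mean and rater expectation. It is an upper guide, hence the range for *f*. The 68.5% also applies to the cord-blood-only group alone; with mesenchymal cells added, the share is 36%.
- **That 2.8 points is the increment this trial seeks.** The plan states no target. The cited regimen also differs in route and cell number: its Group 1 had intrathecal as well as intravenous injections.
- **That control-group change always exceeds the cell increment.** It does for Group 1 (6.2 against 2.8 points) but not for Group 2 (6.2 against 10.9).

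A reader might also infer that the infused families are self-selected. The plan says only that indications are determined at a consultation of doctors, and it does not describe how either group is recruited. The risk is left open, not demonstrated.

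Finally, detailed matching on therapy is too heavy for ten pairs, and an analysis restricted to like-for-like pairs could leave very few children. That objection is right and limits the remedy.

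**Conclusion.** The concern holds in this form: background care in the infused group is unspecified, and background care in either group is neither a comparability factor, nor recorded, nor adjusted for. In a non-randomised 10 v 10 comparison this leaves a plausible confounder of change uncontrolled and, later, unmeasurable. It is more than missing detail, because a stated comparability rule omits a factor that the plan's own precedent held common to all its groups.

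The size is uncertain. If most of the cited control fall was due to therapy, an imbalance of around half would match the difference seen with cord blood cells alone. If only a quarter was, the imbalance would have to be nearly threefold (r = 2.84). These figures rest on proportional benefit, on the assumed share *f*, and on a study with a different regimen. They show that the bias could matter, not that it will occur. The gap should be closed before enrolment.

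**What to change.** 1. In OBJECT OF STUDY and its repeat under STATISTICAL CONSIDERATIONS, state whether the infused group continues the same standard therapy as the controls, and say what that term covers, so that the contrast is defined.
2. In both groups, record current background therapy at baseline (type, approximate weekly hours, whether recently started, psychotropic medication yes or no), and changes in it at each planned visit. Add it to the baseline table.
3. Add one broad category of background-therapy intensity, for example low or high, to the comparability factors used when selecting controls.
4. Report any between-group imbalance, with a descriptive sensitivity comparison that excludes children whose therapy changed materially.

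This is a recording and selection rule and alters no child's care. It costs a short form at visits already planned, some wording, and somewhat slower selection of controls. With ten children per group the sensitivity result can only be descriptive, and a broad category will leave some residual imbalance.

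### Baseline cytokine and immune samples come from children screened as free of recent infection, follow-up samples do not, so the within-group test of laboratory change can pick up ordinary infections

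*Combined protocol and SAP*

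**What the plan says.** The patient exclusion criteria list "Acute respiratory viral and bacterial infections, period less than 1 month after the acute phase". Contraindications are settled early: the Treatment protocol describes "Stage 1 - selection and examination of the patient, determination of indications and contraindications to this method of treatment".

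Baseline laboratory samples come later, in the preliminary examination under Stage 3: "Determination of cytokine levels in peripheral blood: interleukin 1 beta, interleukin 6, tumor necrosis factor alpha, interleukin 8, gamma-interferon - patient" and "Determination of immune status by flow cytometry (SD3; SD4; SD8; SD19; SD16-56) - patient".

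Under Therapy evaluation criteria, "Cytokine profile is assessed 1, 2, 3 months after the first injection", and immune status is repeated 6 months after the last injection. With three injections a month apart (months 0, 1 and 2), that is about month 8.

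For the analysis, Research methods and the closing paragraph of Statistical Considerations both state: "Changes from the start of therapy and after 1, 2, 6, 12 months will be compared using the Wilcoxon criterion". The same sentence plans a Mann-Whitney comparison of the treated and control groups, 10 children each, not randomised. No section makes a follow-up sample depend on infection status, records intercurrent infection or adjusts for it.

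**The concern.** The entry rule works like a run-in that is applied once. Each treated child's baseline is drawn after a screen for recent infection, and each later value is drawn in whatever state the child is in that day. IL-1 beta, IL-6, IL-8, TNF-alpha and interferon gamma are inflammatory markers, so a recent infection could plausibly move them. A paired test takes any such shift as change since therapy began.

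For markers that rise with infection, the error pushes follow-up values up. It could pass for an inflammatory response to the cells, or hide a fall. Because only one end of the comparison is selected, the error does not cancel within pairs. Immune dysregulation is the protocol's rationale, and the link between immune and cytokine profile and disease severity is one of its listed products, so these data are likely to be interpreted. If infection dates are not collected, nobody can judge the problem afterwards.

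**Working it through.** **Inputs from the documents.** Infection-free window at entry: 1 month. Treated children: 10. Cytokine draws after baseline: 3 per child, so 10 x 3 = 30. Immune-status draws after baseline: 1 per child. The plan gives no infection rate, marker variability, effect size or significance level, so it has no figure of its own to reproduce. Everything below is illustrative.

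**Step 1: how often a follow-up sample falls within a month of an infection.** Assume infections occur at random at rate r per child-year. Then P = 1 - exp(-r/12), and the chance of at least one affected cytokine sample per child over months 0 to 3 is 1 - exp(-3r/12).

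| Assumed r | P per sample | Expected of 30 | Expected of 20 (months 1 and 2 only) | At least one per child |
|---|---|---|---|---|
| 2 | 15.4% | 4.6 | 3.1 | 39.3% |
| 4 | 28.3% | 8.5 | 5.7 | 63.2% |
| 6 | 39.3% | 11.8 | 7.9 | 77.7% |

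The column for 20 samples is there because only cytokine months 1 and 2 match the times in the Wilcoxon sentence (1, 2, 6, 12 months). Month 3 and about month 8 do not. If an assumed 7-day acute phase is added to the month, P becomes 19%, 34% and 46%.

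**Step 2: what that does to the tests.** A simulation with no treatment effect used 10 children per group, an assumed baseline to follow-up correlation of 0.5, two-sided tests at an assumed 0.05, and 4,000 runs per setting. Baseline was infection-free, and a share p of follow-up values was raised by a fixed shift. The expected mean change is p x shift. Both Mann-Whitney columns compare changes.

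| p | Shift (SD) | p x shift (SD) | Wilcoxon false positives | Mann-Whitney, controls screened alike | Mann-Whitney, controls not screened |
|---|---|---|---|---|---|
| 0 | 0.5 to 2 | 0 | 0.048 to 0.052 | 0.044 to 0.046 | 0.041 to 0.046 |
| 0.1 | 0.5 to 2 | 0.05 to 0.20 | 0.052 to 0.063 | 0.042 to 0.044 | 0.042 to 0.049 |
| 0.2 | 0.5 | 0.10 | 0.064 | 0.042 | 0.046 |
| 0.35 | 1 | 0.35 | 0.142 | 0.043 | 0.085 |
| 0.5 | 2 | 1.00 | 0.480 | 0.042 | 0.228 |

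The simulation standard error near 5% is sqrt(0.05 x 0.95 / 4000) = 0.003, so the low-p rows are close to nominal. The within-group test is the exposed one. Across all settings run, the between-group test on change stays at 0.039 to 0.047 if controls have the same screen and the same draws.

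**Step 3: whether to drop affected samples from the main analysis.** At 39.3% affected, the number of usable pairs out of 10 at a visit is binomial, and the chance that five or fewer remain is 35%. With five pairs the smallest two-sided exact Wilcoxon p-value is 2/2^5 = 0.0625, so the test could not reach 0.05.

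**The case against.** The strongest reply is that these are secondary data. The Tasks assess efficacy and safety with rating scales, and Expected results names no cytokine change. The rationale speaks of normalising the immune response and does not state a predicted fall in each marker. That stands, and it confines the point to laboratory outcomes; CARS and ATEC are not affected.

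Several stronger readings are tempting, and the documents do not support them:

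- **That controls have no matching draw.** The follow-up draws are timed from injections, which might suggest it, but the Mann-Whitney comparison carries no laboratory exemption. The plan is silent on control sampling. It is also silent on whether controls meet an exclusion list framed as contraindications to the treatment.
- **That no baseline sample can be near an infection.** The screen is at Stage 1 and the sample at Stage 3, with no stated interval. A long gap would weaken the selection.
- **That infection status is certainly ignored at months 1 and 2.** Those draws fall near the second and third injections, where contraindications might be reviewed in practice. This is not written, and it would not cover month 3 or about month 8.
- **That the bias has a known direction for every marker.** Upward is plausible for the inflammatory cytokines. Nothing in the documents supports a direction for the T, B and NK subsets.
- **That a seasonal wave will coincide with time since infusion.** The plan expects that "approximately 4 weeks of accrual will be necessary to enroll 10 participants", so each visit would cluster in a few calendar weeks. The wave itself is conjecture, and it does not fit the constant rate used in Step 1.

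Rank tests and medians also limit the influence of a minority of raised values, as the low-p rows show. What survives is the one-sided screen, the missing record of infection, and a paired test that cannot separate infection from change since therapy.

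**Conclusion.** The asymmetry follows from the documents, and the within-group test of laboratory change is open to it. The size is unknown. The share of affected samples (15% to 39% at an assumed 2 to 6 infections per child-year) describes exposure and does not give the bias in any marker. The error rate of the Wilcoxon test runs from close to nominal when few samples are affected or shifts are small, to 0.14 with 35% affected by 1 SD, and to 0.48 only in the extreme setting of half the samples shifted by 2 SD.

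A reader might infer that the planned laboratory results are certain to be wrong, or that only infection-free samples should be analysed. Neither follows. The first depends wholly on assumed rates and shifts. The second conditions on an event after treatment, which may itself be affected by cells intended to alter the immune response, and it can leave too few pairs to test. The point is a worthwhile and inexpensive correction to secondary outcomes.

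**What to change.** 1. At every cytokine and immune-status draw, baseline included, record the date of any acute infection and flag the sample if it falls within 1 month of one.
2. Keep all samples in the main laboratory analysis. Repeat it without flagged samples as a sensitivity analysis, and report the number of flagged samples by visit and group.
3. State whether controls meet the same infection criterion and have cytokine and immune samples on the same schedule. If they do, rest laboratory inference on the Mann-Whitney comparison of change between groups. If they do not, report laboratory changes as descriptive and do not present them as an effect of the cells.

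The cost is one question per visit and a few sentences in the analysis section. The sensitivity analysis will have fewer children, possibly too few to test, and the laboratory claim becomes weaker if controls are not sampled alike. The change concerns recording and analysis only and does not affect the timing of infusions.
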